#### 4.2.2 Participant Enrollment

##### Modification to Current SANBS Notification Procedures:

All donors with NAT-only infections (HIV, HCV, or HBV) are contacted by letter and telephone to request return to SANBS for additional confirmation of infection. Donors are not informed of the testing results in the letter or during the phone call. Examples of standard notification letters are included (Appendix 1). Currently, all NAT yields are called back to SANBS for follow-up sample collection. SANBS staff does not discuss which virus is suspected based on the NAT yield result. Counseling is done following the testing of the additional samples. A similar letter and approach will be developed and used for persons who are determined to be recently infected based on LAg Avidity testing for HIV and anti-Hepatitis B core negative for HBV.

Currently, donors who test concordant NAT and serology positive for HBV are contacted by telephone if possible and notified of their results with a follow-up letter of the results sent by mail. During the telephone conversation as well as in the letter donors are advised to visit their doctors or local clinic.

Every effort is made to get HIV positive donors back to SANBS for MLO's to do full HIV notification and counseling. Part of this process includes referral to their doctors and/or clinics for further investigation and management. Donors are provided a letter detailing their results which they are urged to take to their doctors.

In order to support the objectives of this study, SANBS will make changes to donor notification procedures:

1. SANBS will seek to inform and counsel all early HBV infections (NAT positive, HBsAg positive or negative and anti-HBc core negative donors) using similar procedures to those used for new HIV infections.
2. SANBS will seek to inform and counsel all of the NAT yields (HIV & HBV). The standard notification letter will be changed to stress that the donor has an early or recently acquired infection. Given the range of testing that is performed on the index donation specimens we expect few notifications to be false positive notifications (See Tables 1 and 2 for standard SANBS index donation testing conducted).
3. All confirmed cases will be urged to seek medical care that conforms to South Africa national treatment guidelines for each infection.

**Cases Objectives 1 and 2:** The prospective enrollment will build on the existing notification mechanism with additional research nurse staff; we will consent and enroll donors during the retest visit during which they will receive pre-test counseling and be informed of the likelihood of being either HIV or HBV positive (**Consent in Appendix 2**). Following the provision of written informed consent and enrollment, participants will complete the ACASI questionnaire. Although

we plan to administer the ACASI questionnaire immediately following enrollment, we will provide study participants the option of returning to enroll and complete the interview at a later date.

For recent HIV (NAT yield and LAg Avidity recent) and recent HBV (NAT yield and HBsAg positive/anti-HBc negative) infections, all eligible cases will be approached for potential enrollment into the study since we anticipate that no more than 50% of those individuals with a recent infection will return to SANBS for their results following an index donation, but that we will have high success in enrolling these individuals into the study

**Controls:** Controls will be identified from among donors who are negative for all infections for which SANBS screens (HIV, HBV, HCV, and syphilis), and who are stratum-matched by blood centre, age within 5 years, population group. (**Consent in Appendix 3**).

We are proposing on-site recruitment of controls, meaning recruitment of potential controls following successful whole blood donation. To enhance our ability to recruit controls that will be able to be *post-hoc* matched on geographic region, population group, and age, we will select donation sites (both fixed and mobile clinics) with donor characteristics that are similar to donors who are incident HIV-positive. Following completion of the donation, we will invite random donors at predetermined collection sites that have similar demographic characteristics to enrolled cases, to participate in the risk factor study by completing the ACASI. Following completion of testing, donors who are negative for all infections for which SANBS screens will be included in the study.

To minimize any community rumors or individual anxieties linking the research to HIV status, recruitment scripts and study informational materials will emphasize that both HIV-positive, HBV-positive, and HIV and HBV-negative participants are being enrolled in order to identify and compare prevailing risk factors among the positive and negative groups. All donors will complete the same ACASI questionnaire.

**Objective 3 Participants:** Selected donors with incident HIV infections who were identified and enrolled during the first two years of Objective 1a and 2a recruitment will be prospectively enrolled into Objective 3 of the study. Participants in Objective 3 will be a subset of Objective 1a and 2a participants who meet eligibility criteria and are willing to participate in this objective. Elite controllers will include those identified in the first 2.5 recruitment years of the study. Donors will be consented and enrolled either during the post-test HIV counseling visit or shortly thereafter timed with Objective 1 enrollment and specimens collected on the day of enrollment and at 3 follow-up visits for CD4, viral load and cytokine profiling as well as PBMC preparations (**Consent in Appendix 4**). The total volume of blood collected at each follow-up visit will not exceed 48 mL.

**Study Locations:** The study will be located in geographic areas within the SANBS catchment where the proportion of donors with HIV and HBV infectious markers is high and where there is documented evidence of good success in notifying donors. We will conduct the study in 5 locations in 4 Provinces; Gauteng (Johannesburg and Pretoria), KwaZulu Natal (Durban), Mpumalanga Province and the Eastern Cape Province. For operational purposes, SANBS divides the Gauteng Province into 3 operational zones, namely “Egoli”, “Vaal” and “Northern”, with Johannesburg the main metropolitan area in Egoli and Pretoria the main metropolitan area in the Northern zone.

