Similarly for HBV, the window period for HBV ID-NAT from the time of potential infectivity that could lead to infection transmission to the ability of current technology to detect is approximately 15 days and HBV ID-NAT positivity precedes Hepatitis B surface antigen (HBsAg) positivity by approximately 17 days (pre HBsAg window period 32 days from potential infectivity) on average. If a donation tests HBV-NAT positive, HBsAg positive, and anti-HBc negative, the infection is also recently acquired (approximately between 32 and 95 days). SANBS identified 476 HBV ID-NAT yields in 5 years however over 50% were also anti-HBc positive, indicating prevalent versus recently acquired infection. Thus, there were approximately 216 true HBV ID-NAT yields in the five year period, resulting in 40-45 individuals per year that were confirmed “window period” donors. In addition SANBS detected 3414 concordant HBV-NAT positive and HBsAg positive donations of which approximately 5% (170) were anti-HBc negative in five years, giving an additional 30-35 incident infections per annum.

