## 4.2 Study Enrollment or Specimen Procurement

### 4.2.1 Screening/Recruitment/Specimen Acquisition

SANBS operations are divided into seven zones, covering eight of the nine provinces of South Africa. Each zone has a Medical Liaison Officer (MLO) who has the primary responsibility for managing donors who test positive for either HIV antibodies or HBV antigen, as well as donors who are antibody/antigen-negative but NAT-positive (NAT yields). Each unit of blood collected by SANBS is tested for HIV, HBV, Hepatitis C Virus (HCV) and syphilis. Donation testing results influence whether standard operational procedures for donor recall and retesting or study protocol procedures will be used. Testing is performed at two testing centres which are located in Constantia Kloof, Gauteng (Johannesburg area) and Pine Town in KwaZulu-Natal (Durban area). Serological assays for anti-HIV, anti-HCV and HBsAg using Abbott Prism are performed simultaneously with nucleic acid testing (NAT) using Ultrio Plus in individual testing format. Donations found repeat reactive by serology but NAT non-reactive or NAT non-repeatable reactive are confirmed using either an HIV Western Blot for HIV or an HBsAg neutralization assay for HBV. If these confirmatory tests are reactive then the donor is classified as a potential serology yield. Donations found negative by serology but repeat reactive by NAT testing are classified as a potential NAT yield. Confirmation of NAT yield status is achieved by assessing the following for HIV: seroconversion in a follow-up sample, detectable viral load, p24 antigen positive result or repeat reactivity on plasma from the fresh frozen plasma unit from the index donation ; and the following for HBV: seroconversion to either HBsAg or anti-HBc on follow up sample, anti-HBc reactivity on current sample, detection of viral load or repeat reactivity on plasma from the fresh frozen plasma unit from the index donation. Figures 1 and 2 provide detailed flow diagrams of the planned study activities for HIV and HBV positive donors, respectively.

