#### 4.5 Assessment and Measurement Procedures

**Detection of Recent HIV Infections by LAg Testing:** LAg avidity testing of concordant HIV RNA and anti-HIV positive donations collected during routine donation will be performed in the SANBS virology reference laboratory to determine whether the donor has recently acquired the infection or whether it is longstanding. LAg avidity incidence assays are focused on measurement of antibody avidity, which increases over time following seroconversion. Antibody avidity is believed to be more robust than antibody titer incidence assays because it is a functional property of maturing antibodies. Duong recently described two novel assays, including two-well avidity index EIA (AI-EIA) and single-well limiting antigen avidity EIA (LAg-Avidity EIA), to measure avidity of HIV antibodies. Key features of the one-well assay are: 1) use of rIDR-M, a multi-subtype recombinant protein that covers the immunodominant region (IDR) of gp41 of HIV-1, group M, 2) the limiting amount of antigen available to allow binding of only high-avidity antibodies, and 3) use of pH 3.0 buffer to further assist dissociation of low avidity antibodies.

**Detection of recent HBV infections by NAT and anti-HBc testing:** Recently infected individuals will be defined by either DNA+/HBsAg-/anti-HBc- or DNA+/HBsAg+/anti-HBc-. Each index donation is screened using NAT and HBsAg and if either or both are repeatable reactive then anti-HBc testing will be performed to eliminate HBV NAT yield occult infections or HBsAg long standing infections. The potential NAT yields will be tested using anti-HBc IgM, total and anti-HBs. The concordant DNA+/HBsAg+ will be tested using anti-HBc total alone.

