**CONFIDENTIAL PERSONAL INFORMATION**

**CONFIDENTIALITY NOTE: This letter is intended only for the confidential use of the intended recipient. The information may be protected by privilege. Please note that any review, dissemination, distribution or copying of this letter is strictly prohibited if you are not the intended recipient. If you have received this letter in error, please desist from reading the contents, notify the sender immediately and destroy this letter**

<Donor's Address>

<Date>

<Donor Number>

<Dear Donor>

Thank you for your recent blood donation. The South African National Blood Service (SANBS) screens all blood donations for certain infections which may be transmitted by blood transfusion, specifically hepatitis B, hepatitis C, HIV and Syphilis. The screening tests used are sometimes over-sensitive and, although an abnormal result may be detected, this does not necessarily mean that you have, or have ever had, an infection.

On your last blood donation the results of a nucleic acid screening test (PCR) was positive. The Nucleic Acid Test is a sensitive test designed to detect early viral infections. Additional tests performed, for the above infections, were however, negative i.e. no corresponding antibodies to any of the above infections were detected.

Because of the discrepancy in these test results, you are urged to revisit a Blood Donor Centre to have another blood sample taken so that the tests can be repeated.

If this result is confirmed, you will unfortunately not be able to continue to donate blood. Because these tests are designed to detect infections which may be transmitted by blood transfusion and, since they may be sexually transmitted, neither you nor your partner may donate blood until this matter has been resolved.

Since it is possible that these results indicate a recent transmissible infection please do not donate blood until this matter is resolved. .

If you have any questions relating to this letter, please contact (MLO and contact number).

Yours sincerely,

Dr.....  
Medical Officer (SANBS)

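### The planned notification letter would describe all HBV NAT yields as early or recent, although the protocol itself classes about 55% of them as prevalent

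*Protocol*

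**What the plan says.** Section 4.2.2 (Participant Enrollment, Modification to Current SANBS Notification Procedures) lists three changes made to support the study. Item 1 concerns early HBV infections, which it defines as NAT positive, HBsAg positive or negative, and anti-HBc negative. Item 2 begins "SANBS will seek to inform and counsel all of the NAT yields (HIV & HBV" and continues: "The standard notification letter will be changed to stress that the donor has an early or recently acquired infection". Item 2 does not mention anti-HBc. It then expects few false positive notifications and refers to Tables 1 and 2.

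Other parts of the protocol bear on who is recent:

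- Section 3 (Background and Significance), on HBV NAT yields over five years: "over 50% were also anti-HBc positive, indicating prevalent versus recently acquired infection".
- Section 4.5, on index donations reactive by NAT or HBsAg: "anti-HBc testing will be performed to eliminate HBV NAT yield occult infections or HBsAg long standing infections".
- Section 4.2.1, among the ways to confirm an HBV NAT yield: "anti-HBc reactivity on current sample".
- Appendix 1, in the existing NAT-only letter: "it is possible that these results indicate a recent transmissible infection".

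**The concern.** Item 2 attaches a statement about recency to a group defined without regard to recency. For HIV this causes no conflict, because the protocol treats HIV NAT yields as incident. For HBV it does, because the NAT-yield group mixes window-period infections with occult or prevalent ones, and anti-HBc is the marker the protocol uses to separate them.

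Followed as written, item 2 would give donors with a long-standing HBV infection a written statement that the infection is early or recently acquired. Appendix 1 already tells donors that the infections screened for may be sexually transmitted. A wrong date for the infection is therefore misleading about when, and through whom, exposure occurred.

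**Working it through.** **1. Who is in the group that item 2 addresses.** Under section 4.2.1 a donation is a potential NAT yield if it is negative by serology and repeat reactive by NAT. The serological screen there consists of anti-HIV, anti-HCV and HBsAg, so anti-HBc plays no part in the definition. Anti-HBc reactivity is, moreover, one of the listed routes to confirming an HBV NAT yield. An anti-HBc-positive donor can therefore be a confirmed member of the group.

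**2. Who is recent under the protocol.** Section 4.5 defines recent HBV as DNA positive and anti-HBc negative, with HBsAg either negative or positive. Item 1 uses the same definition. Section 3 reads anti-HBc positivity as prevalent infection. All three exclude donors whom item 2 includes.

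**3. The protocol's own figures.** The inputs, both from section 3, are "SANBS identified 476 HBV ID-NAT yields in 5 years however over 50% were also anti-HBc positive, indicating prevalent versus recently acquired infection" and "there were approximately 216 true HBV ID-NAT yields in the five year period".

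- Recent share: 216 / 476 = 45.4%.
- Recent per year: 216 / 5 = 43.2, which agrees with the 40–45 a year stated in section 3.
- Not recent: 476 − 216 = 260.
- Share not recent: 260 / 476 = 54.6%, which agrees with the statement that over half were anti-HBc positive.
- Not recent per year: 260 / 5 = 52.

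Among HBV NAT yields, the recency statement would thus be right for about 43 donors a year and wrong, by the protocol's definition, for up to about 52.

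**4. Sensitivity to another count in the protocol.** Table 3 lists 248 HBV NAT-only donors for 2006–2010. Assume that all 248 were recent and that 476 is the matching denominator; the protocol confirms neither, and the periods may differ. The share not recent is then (476 − 248) / 476 = 228 / 476 = 47.9%. About half would still be wrongly described, and section 3 states directly that the share exceeds 50%.

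**5. Whether the result needed to tell the groups apart exists.** Table 2 lists anti-HBc IgM and total on the index specimen of NAT-only HBV donors as standard SANBS testing. Item 2 cites Table 2 but does not use this result to decide who receives the wording.

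**The case against.** **The authors may have meant only anti-HBc-negative donors.** This has some support. Item 1 uses that definition. An earlier paragraph of the same section ties a similar letter to donors found recent by LAg Avidity or by a negative anti-HBc result. The Cases paragraph that follows uses NAT yield as a label for recent HBV. The intention may well be narrower than the text. But item 2 says all NAT yields, item 1 already covers the anti-HBc-negative ones, and an instruction for donor letters should not depend on a qualifier inferred from elsewhere.

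**The protocol expects few false positive notifications.** One could read this as saying that index testing screens out donors who are not recent. Its ordinary meaning is that infection will rarely be absent. A prevalent infection is a true positive, so few false positives is compatible with many false recency statements.

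**The revised letter is not in the document.** This stands. The protocol gives only a one-line instruction, and the final text might be hedged. The point therefore concerns the instruction, which speaks of an infection the donor has, whereas the existing Appendix 1 letter calls recent infection possible pending confirmation.

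**Stronger readings that the documents do not support.** A reader might infer that the letter would draw back donors who cannot be cases. Section 4.2.2 says that all NAT yields are already called back for follow-up samples, so recall is not new. A reader might infer that the HBV case group would be contaminated. Section 4.5 requires anti-HBc negativity, and section 4.2.1 allocates as cases only donors whose confirmatory results show incident infection, so case status and estimates are untouched. A reader might also annualise the three-month count in Table 7, or express the affected donors as a share of all HIV and HBV letters. The protocol gives neither a 2012 anti-HBc split nor a count of letters, so neither extrapolation is secure.

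**Conclusion.** The conflict is real, and it is confined to what HBV donors are told. Item 2, read as written, contradicts item 1 and sections 3 and 4.5 for about 260 of 476 HBV NAT yields (about 55%).

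The figure of about 52 donors a year is an upper bound. It rests on three assumptions: that item 2 applies without an anti-HBc condition, as its text says; that the five-year yield in section 3 carries forward; and that every NAT yield receives the letter. The last is not settled, because section 4.2.1 describes first contact by telephone with a letter if calls fail, while section 4.2.2 describes contact by letter and telephone.

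The matter deserves correction because it concerns written information to infected donors, not because any result of the study is at risk.

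**What to change.** Reconcile item 2 of section 4.2.2 with item 1 and with sections 3, 4.2.1 and 4.5. The recency statement should be limited to donors who meet the protocol's own definition of recent infection; for HBV NAT yields, that means anti-HBc negative on the index sample. Other HBV NAT yields would be notified without it.

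Also reconcile the wording used before confirmation with the conditional wording of the existing Appendix 1 letter, since the NAT-only letter asks the donor to return so that the result can be confirmed.

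The cost is one sentence in section 4.2.2 and a second version of the letter, chosen by an index test result that Table 2 already lists as standard. No additional testing is needed, and the case definition and analyses stay as they are.

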## HIV

The monthly success in notifying donors who are HIV-positive has been documented. These data include both incident and prevalent infections. However, emphasis within SANBS is placed on notifying NAT-yield donors. For the first six months of 2012 cumulative total success in notification was 49% (Table 5). If notification by outside agencies, which can occur for donors who reside in remote locations, is included this proportion increases to 57%. Notification requires that the donor return to SANBS or the alternate notification testing location. This helps us to get past the first barrier to participation in our proposed study; donor return. Because approximately 50% of donors are notified and we are seeking to enroll donors at the time of notification, we believe we are likely to be able to recruit most of the donors who receive notification. However, success in notification is related to the geographic area for two reasons. First is the presence of an active MLO for the region and scale of the geographic area which the MLO has to cover. Table 6 shows that HIV prevalence in the donor population varies by region and rates of successful notification vary by month and by region. During the REDS-III study enrollment period, both a MLO and research assistant will be coordinating efforts to notify and recruit participants for this study. The proportion of successful notifications is expected to increase during the study period. We expect enrollment in our study to be close to the number of successful notifications conducted by SANBS, i.e. approximately 50% of donors with recently acquired HIV.

Table 5. Notification and counseling success rates, all SANBS regions, January-June 2012

All SANBS Zones	Jan 2012	Feb 2012	March 2012	April 2012	May 2012	June 2012	Total
Total HIV Positive	83	97	114	80	134	149	657
Contacted	73	90	97	68	9	143	480
Could not be reached	29	20	19	12	13	38	131
Counseled by SANBS	39	51	48	32	76	76	322
Counseled Outside SANBS	9	5	13	7	10	11	55
Percentage counseled by SANBS	47%	52%	42%	40%	57%	51%	49%

Table 6. Notification and counseling success rates, by SANBS regions, January-June 2012

	January 2012	February 2012	March 2012	April 2012	May 2012	June 2012	Totals for 6 months
KwaZulu Natal (Durban)							
Whole Blood Donations							67429
Number HIV Positive	26	33	38	10	33	32	172
Proportion HIV Positive							0.26%
Number Counseled by SANBS	19	23	22	8	27	25	124
Counseled Outside SANBS	1	1	4	0	0	1	7
Percentage counseled by SANBS	73%	70%	58%	80%	82%	78%	72%
Egoli (Johannesburg)							
Whole Blood Donations							82973
Total HIV Positive	14	29	22	22	22	30	139
Proportion HIV Positive							0.17%
Counseled by SANBS	1	4	9	10	3	5	32
Counseled Outside SANBS	4	8	6	2	10	5	35
Percentage counseled by SANBS	29%	28%	27%	9%	45%	17%	25%
Vaal							
Whole Blood Donations							57537
Total HIV Positive				21	23	19	63
Proportion HIV Positive							0.11%
Counseled by SANBS				11	17	12	40
Counseled Outside SANBS				0	0	2	2
Percentage counseled by SANBS	No MLO	No MLO	No MLO	52%	74%	63%	63%
Eastern Cape							
Whole Blood Donations							36070
Total HIV Positive	16	14	17	4	13	16	80
Proportion HIV Positive							0.22%
Counseled by SANBS	6	5	4	2	3	5	25
Counseled Outside SANBS	3	0	5	0	0	1	9
Percentage counseled by SANBS	38%	36%	24%	50%	23%	31%	31%
Free State/Northern Cape							
Whole Blood Donations							37642
Total HIV Positive	12	14	9	10	9	7	61

Proportion HIV Positive							0.16%
Counseled by SANBS	7	11	9	9	9	5	50
Counseled Outside SANBS	3	1	0	1	0	1	6
Percentage counseled by SANBS	58%	79%	100%	90%	100%	71%	82%
Mpumalanga							
Whole Blood Donations							42493
Total HIV Positive	16	20	22	13	23	24	118
Proportion HIV Positive							0.28%
Counseled by SANBS	4	3	3	7	14	13	44
Counseled Outside SANBS	2	2	2	1	1		8
Percentage counseled by SANBS	25%	15%	14%	54%	61%	54%	37%
Northern (Pretoria)							
Whole Blood Donations							79499
Total HIV Positive	23	15	30	13	18	21	120
Proportion HIV Positive							0.15%
Counseled by SANBS	7	9	13	3	9	11	52
Counseled Outside SANBS	4	1	3	1	1	1	11
Percentage counseled by SANBS	30%	60%	43%	23%	50%	52%	43%
All Locations							
Whole Blood Donations							404842
Total HIV Positive	107	125	138	93	141	149	753
Proportion HIV Positive							0.19%
Counseled by SANBS	44	55	60	50	82	76	367
Counseled Outside SANBS	17	13	20	5	12	11	78
Percentage counseled by SANBS	41%	44%	43%	54%	58%	51%	49%

